This is a PMCF study designed to collect and evaluate outcome measures and adverse event data. A maximum of three sites will contribute to this study. Each Investigator will be skilled in external fracture stabilization and experienced in implanting the devices included in this study, as determined by the Sponsor.

Each Investigator will be responsible for obtaining IRB approval as required prior

to conducting the study. In order to avoid potential selection bias, each Investigator will offer study participation to each consecutive eligible patient presenting need for temporary stabilization with the FastFrame External Fixation System - Knee Spanning or Damage Control Kits. Eligible candidates who express interest in study participation will be offered **Informed Consent**. All potential study subjects will be required to participate in the Informed Consent process and will not be considered enrolled in the study until the candidate has signed and dated the IRB approved **Informed Consent** and the study device has been implanted.

VIII. Study Population

A maximum of three (3) sites in the United States will contribute to this study. No randomization will take place, as all subjects must receive the study device that best treats their clinical need.

The study population for primary statistical analysis will be comprised of all enrolled subjects who satisfy the Inclusion/Exclusion Criteria outlined in the protocol. In order to avoid potential selection bias, each Investigator will offer study participation to each consecutive eligible patient presenting as a candidate. Eligible candidates who express interest in study participation will be offered **Informed Consent**. Inclusion/Exclusion Criteria should not be evaluated until the **Informed Consent** has been completed.

Inclusion Criteria

- Patient must be 18 years of age or older
- Patient must be treated with either the Knee Spanning or Damage Control FastFrame External Fixation System according to the indications stated in this protocol*

*EEA Indications (a subset of the cleared US indications):

The FastFrame External Fixation System – Knee Spanning Kit is indicated for use in treatment of long bone (distal femur, proximal tibia) fractures. Specifically, the system is intended for temporary stabilization of open or closed fractures about the knee, typically in the context of polytrauma or where open or alternative closed treatment is undesirable or otherwise contraindicated.

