Informed Consent will be completed by patients who are able to consent themselves or if unable, have a proxy available. The patient will be given an adequate amount of time to read the consent and ask questions to the investigator and/or research staff. If the patient agrees to participate in the study, he/she will sign the consent form. If a patient is unable to consent for him/herself due to the need for immediate surgical intervention, a proxy signature may be used to consent on the patient's behalf. The following individuals may serve as a proxy on behalf of the patient during the Informed Consent process: legal guardian, proxy health care agent, or a close family member of the patient. The relationship of the proxy to the patient must be documented on the **Informed Consent Log**. If the patient becomes able to consent himself or herself at any point in time, a re-consent must occur with the patient's signature. Due to the immediate surgical intervention regarding the study operation, Informed Consent can be obtained after surgery, but no later than the follow-up visit defined in this protocol.

Informed Consent/Enrollment Log

An **Informed Consent/Enrollment Log** will be maintained at the site throughout the course of the study. The purpose of the log is to provide documentation that all enrolled study subjects and/or proxies as defined in the Informed Consent Process section of this protocol underwent the Informed Consent process, signed and dated the IRB approved **Informed Consent**, and were provided with a copy of the fully executed consent with all required signatures. All candidates who sign and date the approved **Informed Consent** for the study must be entered in the

log. If a subject signs and dates additional Informed Consent(s) after enrollment (i.e., due to a protocol amendment, protocol revisions, re-consent after surgery, etc.), subsequent signings will also be recorded in the log. If a proxy signature is used, the relationship of the proxy to the patient must be documented. The **Informed Consent/Enrollment Log** will be filed in the site Regulatory Binder for the study.

Subject Enrollment

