Once the **Informed Consent** has been signed and dated by the subject (or proxy as defined in the Informed Consent Process section of this protocol) and a FastFrame System has been implanted, the subject will be considered enrolled in the study. A unique case identification number (Case ID) will be assigned to each participating subject (bilateral subjects will be assigned a unique case ID number for each temporary stabilization procedure). This unique case ID number will be used throughout the study for identification. Case ID numbers will be assigned consecutively in ascending order per site, with the starting number for a given site defined by the Sponsor.

Monitoring Log

The **Site Monitoring Visit Log** will be maintained throughout the course of the study. The log will contain the visit date, monitor name/signature and the purpose of the visit (i.e. site initiation, onsite interim monitoring (as applicable), site closeout, etc.). The **Site Monitoring Visit Log** will be filed in the site Regulatory Binder for the study.

Delegation of Authority/Site Signature Log

A **Delegation of Authority/Site Signature Log** will be maintained throughout the study and will contain the names, initials, signatures, and study responsibilities of all site personnel and designees involved in the study procedures and data collection. The Investigator is responsible to sign and date the log after any updates to the log to acknowledge the change(s). The **Delegation of Authority/Site Signature Log** will be filed in the site Regulatory Binder for the study.

Baseline Procedure

Subjects will be enrolled prior to undergoing a procedure using the FastFrame External Fixation System, therefore allowing for the capture of baseline data to be

collected on the following CRFs:

- **Inclusion/Exclusion Criteria**
- **Demographic Evaluation**
- **Protocol Deviation, if applicable**

Operative/Immediate Post-Operative Procedure

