The Investigator should ensure the accuracy, completeness, legibility, and timeliness of data reported to the Sponsor in accordance with this protocol. The Investigator or Designee will provide periodic reports to their IRB as required to maintain IRB approval throughout the study, and will provide any required final reporting to the IRB upon study completion/termination. A copy of all IRB re-approval letters must be submitted to the Sponsor. If the IRB terminates or suspends its approval of the study, the Investigator or Designee will suspend study-related activities and will promptly notify the Sponsor. The Investigator should also promptly provide written reports to the Sponsor and the IRB regarding any changes significantly affecting the conduct of the study, and/or increasing risk to the subjects.

Retention of Records

For this study, study records must be retained by the Investigator or Designee for a minimum of 15 years from the Investigator's study termination date, or per applicable regulatory and/or IRB requirements (whichever time period is greater). Measures shall be taken to prevent accidental or premature destruction.

Study records are defined as the all information in original records, certified copies of original records of clinical findings, observations or other activities in a clinical study, including source data initially recorded in an electronic format, necessary for the reconstruction and evaluation of the clinical study. This may include but is not limited to: hospital records, clinic records, laboratory notes, device accountability records, photographs, radiographs, subject casebooks, regulatory records, signed informed consents, and all other study-related documents.

Management of Incurrent Events

Failure to Obtain Informed Consent

Study data will not be collected until the **Informed Consent** has been signed and dated by the candidate. If a candidate does not wish to participate (does not sign and date the ICF), data for that candidate will not be collected for this study.

Adverse Events

See Safety Management – Medical Events/Adverse Events Section of this protocol for additional information regarding adverse event classifications.

Reporting and Documentation of Adverse Events and Adverse Device Effects

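### Consent may follow the outcome and no record of all treated patients is required, so the plan specifies no means to prevent or detect outcome-dependent enrolment

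*Combined protocol and SAP*

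**What the plan says.** Sections VII and VIII name one measure against selection bias. In Section VIII it reads: "In order to avoid potential selection bias, each Investigator will offer study participation to each consecutive eligible patient presenting as a candidate". Section X repeats the consecutive offer without giving that purpose. No other measure is named.

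On timing, Section X makes two statements that do not fit together:

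- Informed Consent Process: because surgery is immediate, "Informed Consent can be obtained after surgery, but no later than the follow-up visit defined in this protocol". That visit is the device exchange (Synopsis, Length of Study; Section X, Post-Operative Follow-Up Procedure), typically 2 to 4 weeks on.
- Baseline Procedure: "Subjects will be enrolled prior to undergoing a procedure using the FastFrame External Fixation System".

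On records, Section X describes one recruitment log, the Informed Consent/Enrollment Log. Its role concerns consent: "The purpose of the log is to provide documentation that all enrolled study subjects and/or proxies" went through the process. The entry rule is "All candidates who sign and date the approved Informed Consent for the study must be entered in the" log. Section XI (Failure to Obtain Informed Consent) adds that, where a candidate does not wish to take part, "data for that candidate will not be collected for this study". No section asks for a count of patients treated with a FastFrame kit, of patients approached, or of refusals.

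The primary analysis population is the enrolled subjects who meet the criteria (Section VIII). Section XV tests their success rate against 95% less a 10-point margin.

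**The concern.** The primary endpoint counts device-related events and device deficiencies up to exchange of the frame. A patient first approached at the exchange visit has already completed the observation period, and the person making the approach can know the result. A site could follow the consent and logging rules to the letter and still enrol patients partly according to how the frame performed. This need not be deliberate: a patient whose frame was removed early may simply never be asked.

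There is no control arm to share such a bias. The result is one proportion set against a fixed figure, so it depends directly on who enters. If patients with device failures enter less often than others, the success rate is too high. With no treated-patient denominator, the report could not show whether that had happened or support the description of the cohort as consecutive.

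**Working it through.** **Inputs from Section XV and the Synopsis.** Expected success 95%; margin 10 points, so the null success rate is 0.95 − 0.10 = 0.85; one-sided exact binomial test at 0.05; 60 evaluable subjects; about 80% power.

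**Reproducing the plan's figure.** The smallest number of successes x with P(X ≥ x | n = 60, p = 0.85) ≤ 0.05 is 56, so at most 4 failures are allowed. The exact type I error is 0.0424 and power at 95% success is 0.8197. The one-sided 95% exact lower limit is 0.854 at 56/60 and 0.833 at 55/60, which agrees with the rule. The stated 60 subjects and approximate 80% power reproduce.

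**Effect of selective entry.** Let p be the true failure rate and r the enrolment rate of failing patients relative to the others. The failure rate among enrolled subjects is

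q = p·r / (p·r + 1 − p)

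and the chance of passing is P(at most 4 failures | 60, q). With p = 0.15:

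| r (assumed) | q | Chance of passing |
|---|---|---|
| 1 | 0.150 | 4.2% |
| 0.9 | 0.135/0.985 = 0.137 | 7.3% |
| 0.8 | 0.120/0.970 = 0.124 | 12.1% |
| 0.75 | 0.1125/0.9625 = 0.117 | 15.5% |
| 0.5 | 0.075/0.925 = 0.081 | 45.8% |

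**What r would require.** Only a patient who has not consented when the frame fails can be selected on that failure. If s is the share of failures that occur before consent and r_late is the relative enrolment of those patients, then r = 1 − s(1 − r_late).

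- s = 20%, half of them enrolled: r = 1 − 0.2 × 0.5 = 0.9
- s = 50%, half of them enrolled: r = 1 − 0.5 × 0.5 = 0.75
- s = 50%, none enrolled: r = 1 − 0.5 × 1 = 0.5

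The documents give neither s nor r_late.

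**Fragility of a pass.** Adding unenrolled failures to an observed pass and repeating the exact test against 0.85:

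- 56/60 passes (p = 0.042); one missed failure gives 56/61, p = 0.089.
- 57/60 passes (p = 0.015); two missed failures give 57/62, p = 0.081.
- 60/60 is overturned by five missed failures: 60/65, p = 0.062.

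**The case against.** The strongest reply is that late consent is an exception for urgent surgery. Section IV schedules consent on Day 1, Section X provides for proxy consent, and Baseline Procedure expects enrolment before the operation. If most patients consent early, few failures can be selected on, r stays near 1 and the distortion is small. That limits the likely size, and it is why the range matters more than any single figure. It does not close the gap, because the late limit is the exchange visit and the two statements in Section X are left unreconciled.

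Four stronger readings are tempting, and the documents do not support them.

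- *That the eligibility rule causes the selection.* Section VIII says "Inclusion/Exclusion Criteria should not be evaluated until the Informed Consent has been completed", which sits awkwardly with an offer to eligible patients. This is loose wording. Section VII gives a usable trigger for the offer, namely need for stabilization with one of the kits, and deferring formal assessment limits discretionary screening-out rather than enabling it.
- *That Section XI forbids any record of patients who do not sign.* It concerns study data and candidates who do not wish to take part. It says nothing of patients never approached and does not clearly rule out a de-identified count. The log rule likewise sets a minimum content.
- *That selection could not be prevented or detected at all.* Consents are dated, subjects are identified by surgery date among other items (Section XI), and adverse event forms carry onset dates, so late consent among enrolled subjects can be found. Device accountability records are listed for retention, and any onsite monitors may see other relevant documents (Section XIII). A reconciliation with device use is possible, but the plan does not specify one.
- *That patients who die or are transferred before being asked are hidden failures.* Neither is necessarily a device failure.

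It is also fair to say that a log of kit use shows coverage and not the outcomes of unenrolled patients. Reporting by consent timing is therefore needed beside it.

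**Conclusion.** The concern holds in this form: consent may be given once the primary outcome is known, the text on enrolment timing contradicts itself, and no record of all treated patients is required. Consecutive enrolment is therefore asserted but cannot be verified from anything the plan specifies.

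At 15% true failures, the chance of passing goes from 4.2% to between 7.3% and 15.5% for relative enrolment of 0.9 to 0.75. Even the mildest case shown exceeds the stated 5%. A reader might take the 45.8% at 0.5 as the expected size. It is not: it needs, for example, half of all failures to precede consent and none of those patients to be enrolled. All values of r are assumptions. The calculation also assumes exactly 60 evaluable subjects and that a failure is a subject with a primary-endpoint event. Nothing in the documents shows that selection has occurred. The change should be made because it is inexpensive and determines what the report can conclude.

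**What to change.** 1. **Timing.** Reconcile Informed Consent Process and Baseline Procedure in Section X, so that the plan says in one consistent way when consent and enrolment occur.
2. **Log.** Extend the Informed Consent/Enrollment Log to one de-identified line for each Knee Spanning or Damage Control kit used at the site during enrolment: surgery date, kit, adult and within the protocol indications (yes/no), offered (yes/no and date), consent date, and reason not enrolled. Reconcile it with kit and lot usage. State that the rule in Section XI (Failure to Obtain Informed Consent) does not preclude this line.
3. **Reporting.** Give enrolled over potentially eligible treated patients, by site and kit. The adult-and-indication column keeps uses outside the protocol out of that denominator. Report the success rate separately for subjects who consented before surgery, after surgery but before any device event, and after an event. Where that event counts toward the primary endpoint, subjects in the last group are failures by construction, so show the group as a count as well. Call the cohort consecutive only if the log supports it.

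The cost is some clerical time at no more than three sites and IRB agreement to the de-identified line. The sample size and the test are unchanged.

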All surgeries will take place following the standard, approved surgical technique. During the course of the surgery, a **Surgical Device** CRF must be completed documenting the part and lot numbers of the implants. The FDA cleared or other local government regulatory body approved instructions for use and surgical technique must be followed for this product. Please refer to the latest versions of these documents on the Zimmer Biomet website, contact your local Clinical Study Manager, or contact a Zimmer Biomet sales associate for additional details. The following operative data will be collected on the following CRFs:

- **Operative Record**
- **Surgical Device**
- **Protocol Deviation, if applicable**
- **Adverse Event Report, if applicable**
- **Physician Imaging Assessment**
- **Photographs of study device in two (2) planes (A/P and lateral)**

Photographs will be stored in the Subject Binder as part of their casebook. Please write the Subject Case ID Number, Subject Initials, and Date (YYYY-MM-DD) on the photographs. If an adverse event occurs, an **Adverse Event Report** CRF will also be completed. See Management of Incurrent Events for additional details. Reason(s) for study completion must be documented on the **Study Completion** CRF.

Post-Operative Follow-Up Procedure

Post-operative clinical assessment will be conducted at the device exchange follow-up visit after the procedure. The device exchange of a FastFrame External Fixation Kit typically occurs 2-4 weeks after surgery. The following

CRFs will be collected at the follow-up visit when the study device is removed from the subject:

- **Physician Follow-Up Assessment**
- **Protocol Deviation, if applicable**
- **Adverse Event Report, if applicable**
- **Physician Imaging Assessment, if required**
- **Photographs of study device in two (2) planes (A/P and lateral), if required**
- **Study Completion**

Subjects will be followed post-operatively until the FastFrame External Fixation Kit is exchanged with another device or unless the primary endpoint is reached prior. Unless the study is otherwise closed, data will continue to be collected until the subject completes the study per the protocol, voluntarily withdraws from the study, is withdrawn from the study by the Investigator, is lost to follow-up, undergoes revision to remove a study device (does not include device removal as part of standard treatment), or expires.

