This study protocol must be submitted to and approved by the Investigator's Institutional Review Board (IRB). A copy of the IRB approval letter must be submitted to the Sponsor. The letter should identify the following:

- Protocol name and/or number
- Date of IRB meeting (if available)
- Date of approval
- Date of expiration
- Signature of IRB

ClinicalTrials.gov Registration

The Sponsor will be responsible for registering this study on www.ClinicalTrials.gov if required by local and national regulations.

Clinical Data Collection/Submission

Summary of Case Report Form Data Collection

Study data will be collected on source documents, which may include study-specific worksheets provided by the Sponsor. For subjects undergoing temporary stabilization using multiple FastFrame External Fixation Kits, separate case report forms must be completed for each operative device.

The following source document/CRF completion guidelines should be followed:

- Complete carefully and accurately
- Complete header information consistently across all case report forms for each individual study subject
- Be sure that data on the source documents match that which is entered through the EDC system
- Use the study subject's unique Case ID number assigned as instructed
- Do not provide information that is not requested on the CRFs
- Ensure that all fields are completed. For fields completed by the subject, efforts should be made to obtain any missing responses prior to the subject completing their visit.

Data Submission

Completed CRFs will be submitted directly to the Sponsor by electronic data capture and submission via a method approved by the Sponsor. Every effort must be made to ensure data submission to the Sponsor is made within 30 days of the visit completion.

Quality Assurance of Data

The Investigator should ensure the accuracy, completeness, legibility, and timeliness of the data reported to the Sponsor in the CRFs and in all required reports. Data reported on the CRF, which are derived from source documents, should be consistent with the source documents or the discrepancies should be explained. All electronic systems used to create, modify, maintain, or transmit electronic study records will be validated. The Sponsor will maintain quality control systems, in accordance with the Sponsor's policies and procedures.

Reporting Requirements

Investigator Reporting Responsibilities

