Adverse Events and Adverse Device Effects have to be documented on the Adverse Event Report form over the whole time of the investigation including information on the date of onset, treatment and resolution, as well as assessment of both the seriousness and the relationship to the study device. Further, the outcome of complications has to be documented and any changes in outcome are to be updated during the course of the study. In case of early termination of the study, further follow-up of the patient shall proceed according to the hospital's standard procedure.

Reporting and Documentation of Serious Adverse Events, Serious Adverse Device Effects, and Device Deficiencies

Serious Adverse Events and Serious Adverse Device Effects have to be **reported to the Sponsor as soon as possible**. The incidence has to be documented on the Adverse Event Report form over the whole time of the investigation including information on the date of onset, treatment and resolution, as well as assessment of both the seriousness and the relationship to the study device based on the evaluation of the Investigator. The outcome of such complications has to be documented and any changes in outcome have to be updated during the course of the study. In case of early termination of the study, further follow-up of the study subject shall proceed according to the hospital's standard procedure.

Device Deficiencies that did not lead to an adverse event but **could have led** to a medical occurrence if suitable actions had not been taken, if intervention had not been made or if circumstances had been less fortunate shall be **reported to the Sponsor as soon as possible**, as well.

The **Investigator** is responsible for reporting all SAEs, SADEs and Device Deficiencies that could have led to a SADE to the Institutional Review Board if required by national regulations or by the IRB.

Schedule

In the event that early removal of one or more of the study related components is necessary, the Investigator will determine the best treatment and/or revision method for the subject. Once the revision surgery has been completed, the Investigator or

qualified Designee must complete an **Adverse Event report** CRF as well as a **Study Completion** CRF terminating the subject from the study. Relevant radiographs and/or photographs of the explanted component(s) will be sent to the Sponsor.

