Study subject participation is expected to end upon completion of the subject's device exchange follow-up visit unless the subject voluntarily withdraws from the study, is withdrawn from the study by the Investigator, is lost to follow-up, undergoes an unplanned revision to remove a study device, or expires. Reason(s) for study completion must be documented on the **Study Completion CRF**.

If the Sponsor decides to terminate the study early, the Sponsor will inform the Investigators of the reason for early study termination. It is the responsibility of the Investigators to inform their IRB as applicable according to local and national laws/regulations.

Modification of the Protocol

All amendments to this clinical protocol shall be agreed to by the Sponsor and be recorded with a justification for the amendment prior to implementation. Approval of the applicable IRB must be obtained prior to implementation, if required according to the local and/or national laws/regulations.

XII. Safety Management – Medical Events/Adverse Events

Adverse events are required to be reported on the **Adverse Event Report CRF**. The completed **Adverse Event Report** CRF must be submitted to the Sponsor in a timely manner. The Investigator or Designee will also promptly provide the Sponsor with any additional requested information required for the Sponsor to comply with regulatory requirements. If applicable per their reporting requirements, the Investigator or Designee will also report applicable adverse event(s) to their IRB.

The following definitions are from ISO 14155:2020 and Regulation (EU) 2017/745: Safety reporting in clinical investigations of medical devices.

Classification of the Event

Adverse Event (AE):

An adverse event is any untoward medical occurrence, unintended disease or injury, or untoward clinical signs (including abnormal laboratory findings) in subjects, users or other persons, whether or not related to the investigational medical device and whether anticipated or unanticipated.

Note 1: This definition includes events related to the investigational medical device or the comparator.

Note 2: This definition includes events related to the procedures involved.

Note 3: For users or other persons, this definition is restricted to events related to investigational medical devices or comparators.

Serious Adverse Event (SAE):

A Serious Adverse Event is any adverse event that:

- a. led to death.

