Statistical methodology will consist of summarizing collected data descriptively. Categorical data (i.e., gender or race) will be summarized using counts and percentages, and 95% CI, over the time periods of interest. Continuous data, such as age, will be summarized by using means, medians, standard deviation, minimum, maximum, and 95% CI over the time periods of interest. Implant survival will be summarized using a Kaplan-Meier method and presented with rates (as percentages) and confidence intervals.

Sample Size

Calculation of sample size is based on previously published literature involving longitudinal data collection on temporary external fixation. Assuming a power level of 80% and an alpha level of significance of 0.05 ($\alpha = 0.05$), calculations were performed in order to determine the sample size needed for study significance using the following hypothesis test:

The hypothesis will be tested by the exact binomial test:

$$H_0: E_1 - E_0 \leq -\delta E$$

$$H_a: E_1 - E_0 > -\delta E$$

where:

$E_0 = 95\%$, the expected success rate

E_1 = the success rate in the FastFrame System treatment group

$\delta E = 0.10$, non-inferiority margin

In addition, one-sided 95% exact confidence Interval (CI), lower limit of the success rate, will be calculated.

Based on the hypothesis test above, 60 subjects will provide approximately 80% power for the one-sided exact binomial test at 0.05 significant level. The sample size was calculated using SAS for Windows version 9.4.

It was determined that the complication rate of devices comparable to the FastFrame External Fixation System is approximately 5%. Utilizing this figure, the power, and alpha level of significance, a sample size total (without any subjects becoming lost to follow-up) of 60 was obtained. Finally, in order to maintain a sample size large enough for statistical significance an estimated, 90% subject return rate is assumed for the duration of the device exchange follow-up visits. These lost to follow-up patients increase the sample size requirements to 66 subjects (after rounding up).

Visit	Subjects remaining in the study
Baseline	66
Follow-Up	60

XVI. Quality Control & Quality Assurance

The study is conducted in accordance with the Declaration of Helsinki and the ISO 14155:2020 and Regulation (EU) 2017/745.

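### Does keeping records per frame while wording the exit rules per subject leave two-frame subjects wrongly followed or wrongly counted?

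*Combined protocol and SAP*

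**What the plan says.** Records are kept below the level of the person. Section X, Subject Enrollment, states that "bilateral subjects will be assigned a unique case ID number for each temporary stabilization procedure". Section XI, Summary of Case Report Form Data Collection, adds for subjects with several kits that "separate case report forms must be completed for each operative device".

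The exits are worded for the person:

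- Section X, Post-Operative Follow-Up Procedure, follows subjects until the kit is exchanged "or unless the primary endpoint is reached prior". Its list of exits includes a subject who "undergoes revision to remove a study device (does not include device removal as part of standard treatment".
- Section XI, Schedule, has early removal of components end in a Study Completion "CRF terminating the subject from the study".
- Section XI, Study Termination: "Study subject participation is expected to end upon completion of the subject's device exchange follow-up visit".

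The analysis is stated in subjects. Section VIII: "The study population for primary statistical analysis will be comprised of all enrolled subjects" who meet the entry criteria. The Synopsis speaks of 66 patients, and Section XV of 60 subjects for the exact binomial test and 66 to be enrolled. Section XV also says: "Implant survival will be summarized using a Kaplan-Meier method and presented with rates (as percentages) and confidence intervals". It does not name the unit for that curve.

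**The concern.** Taken word for word, the exit rules allow two unwelcome outcomes.

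1. A subject has two frames and one fails or is exchanged. The subject leaves the study and the other frame, still in place, is no longer observed. The primary endpoint covers the frequency as well as the incidence of device-related events up to exchange, so later events on that frame would be missed.
2. Each frame is closed as its own case. Both are then observed, but two cases of one person could enter the analysis as if independent. Per-frame intervals would be too narrow, and one person might take two of the 60 places.

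The indications cover femur and tibia fractures, typically in polytrauma, so two-frame subjects are a real possibility. An analysis unit chosen after the events are known would also invite doubt.

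**Working it through.** **Inputs from the plan (Section XV).** n = 60, expected success 0.95, margin 0.10, hence null success 0.95 − 0.10 = 0.85; one-sided α = 0.05; power about 80%.

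**Assumed inputs (not in the documents).** k two-frame subjects among 60; failure probability p = 0.05 per frame; within-person correlation ρ from 0 to 0.8, or to 1 where stated.

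**1. The plan's own figure.** The smallest success count with exact size at or below 0.05 is 56 of 60, that is, at most 4 failures.
- Size: P(X ≥ 56 | 60, 0.85) = 0.0424
- Power: P(X ≥ 56 | 60, 0.95) = 0.820

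The stated 60 reproduces, with the person as the unit.

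**2. Which unit does an exit close?** Post-Operative Follow-Up Procedure lists Study Completion and the Physician Follow-Up Assessment among the CRFs collected when the study device is removed. Section XI requires separate CRFs for each operative device. Together these give each frame its own removal visit and its own completion form. The subject-level phrase under Schedule then reads as wording written with one frame in mind.

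**3. Effect on the exact test.** Under exit per frame nothing is lost. Even under subject-level exit after a primary event, a missed event on the other frame belongs to a person who has already failed, so the failure count is the same.

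**4. Events missed under the subject-level reading.**
- After the partner fails: P(both fail) = p² + ρp(1−p) = 0.0025, 0.02625, 0.0405 at ρ = 0, 0.5, 0.8. If every second failure comes after the first revision, k = 6 loses 6 × P(both) = 0.015, 0.158, 0.243 of 66 × 0.05 = 3.30 expected failures.
- After a first planned exchange: take independent exchange days, uniform over days 14 to 28 (mean 21, mean gap 14/3 days), and a constant failure rate. The loss at k = 6 is roughly 6 × (0.05/21) × (14/3) = 0.067 expected failures, slightly less once earlier failures are removed.

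These are separate scenarios, and neither is an upper bound on all losses.

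**5. Kaplan-Meier by frame (k = 6).** If the partner is censored at the first failure and failure times within a pair are independent and uniform, simulated failure is 5.0%, 4.8%, 4.65% at ρ = 0, 0.5, 0.8, against a true 5.0%. If both frames fail at the same moment there is no shift. For scale, the exact 95% interval for 3 failures in 66 frames is 0.9% to 12.7%.

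**6. Ignoring the pairing in per-frame intervals.** Design effect = 1 + 2kρ/(60 + k). At k = 6, ρ = 0.8: 1 + 9.6/66 = 1.145, and √1.145 = 1.07. At k = 10, ρ = 0.8: 1 + 16/70 = 1.229, and √1.229 = 1.11.

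**7. Sixty frames tested as independent, against the plan's wording.** Exact convolution of single frames and correlated pairs, threshold 56:

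| Pairs among 60 frames | Size, ρ = 0 | ρ = 0.5 | ρ = 1 |
|---|---|---|---|
| 3 | 0.042 | 0.046 | 0.050 |
| 6 | 0.042 | 0.050 | 0.058 |
| 12 | 0.042 | 0.058 | 0.075 |

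**8. Power if the 5% is a per-device rate.** The documents do not settle this. A two-frame subject then fails with probability 2p − P(both) = 0.0975, 0.0738, 0.0595 at ρ = 0, 0.5, 0.8. Subject-level power is 0.795 to 0.815 at k = 3 and 0.769 to 0.810 at k = 6. The size at a subject-level null of 85% is unaffected.

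**The case for a change.** The strongest case for a change is that the text under Schedule ends the subject's participation, not the case, and that per-frame exit still leaves the combination rule unwritten. The extra Case ID goes only to bilateral subjects, so two kits on one side rest on the separate CRFs alone. There is also one route by which the test could change. If participation ended at the first planned exchange and the other frame failed later, the missed event would belong to a person counted as a success. Finally, with many strongly correlated pairs treated as independent, the size would pass 0.05.

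Part of this stands. The wording is uneven, and no sentence says that a subject fails if any frame fails. But the first-exchange route needs the reading that the per-device forms argue against, and it loses about 0.07 expected failures in the scenario above. The inflated size needs analysts to count frames where the plan counts subjects. Counting a person with a primary event on any frame as one failure is the natural reading of a subject-level success rate. The two cases of one person can also be matched: the opening of Section XI says reports typically identify subjects by initials, Case ID, surgery date, operative side and date or year of birth.

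Stopping follow-up at the primary endpoint applies to single-frame subjects too, so it is a separate question. The sentence after it continues data collection to a list of exits that does not name the primary endpoint.

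**Conclusion.** This is missing detail that analysts can fill sensibly, joined to exit wording written with one frame in mind. The per-device forms point to exit frame by frame, and the sample size and primary population already count each person once. On that reading the exact test stands as planned: at most 4 failures in 60, size 0.042, power 0.820.

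What remains touches descriptive per-frame summaries. At an assumed 6 two-frame subjects and correlation up to 0.8, the standard-error factor is at most 1.07 and the Kaplan-Meier shift is 0.35 points or less in the scenario shown, against an interval running from 0.9% to 12.7%. These figures rest on an assumed two-frame share, correlation and timing, so they are scenarios and not bounds. If two-frame subjects proved common, the per-frame intervals would need to allow for pairing, which can be done at analysis. No change to the plan is needed.
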